## 10.7. Appendix 7: ECG Findings of Potential Clinical Concern

ECG Findings That May Qualify as Adverse Events

• Marked sinus bradycardia (rate <40 bpm) lasting minutes.

• New PR interval prolongation >280 msec.

• New prolongation of QTcF to >480 msec (absolute) or by <math>\geq 60</math> msec from baseline.

• New-onset atrial flutter or fibrillation, with controlled ventricular response rate: ie, rate <120 bpm.

• New-onset type I second-degree (Wenckebach) AV block of >30 seconds' duration.

• Frequent PVCs, triplets, or short intervals (<30 seconds) of consecutive ventricular complexes.

ECG Findings That May Qualify as Serious Adverse Events

• QTcF prolongation >500 msec.

• New ST-T changes suggestive of myocardial ischemia.

• New-onset left bundle branch block (QRS >120 msec).

• New-onset right bundle branch block (QRS >120 msec).

• Symptomatic bradycardia.

• Asystole:

• In awake, symptom-free patients in sinus rhythm, with documented periods of asystole <math>\geq 3.0</math> seconds or any escape rate <40 bpm, or with an escape rhythm that is below the AV node;

• In awake, symptom-free patients with atrial fibrillation and bradycardia with 1 or more pauses of at least 5 seconds or longer;

• Atrial flutter or fibrillation, with rapid ventricular response rate: rapid = rate >120 bpm.

• Sustained supraventricular tachycardia (rate >120 bpm) ("sustained" = short duration with relevant symptoms or lasting >1 minute).

- Ventricular rhythms >30 seconds' duration, including idioventricular rhythm (HR <40 bpm), accelerated idioventricular rhythm (HR 40 bpm to <100 bpm), and monomorphic/polymorphic ventricular tachycardia (HR >100 bpm [such as torsades de pointes]).
- Type II second-degree (Mobitz II) AV block.
- Complete (third-degree) heart block.

#### **ECG Findings That Qualify as Serious Adverse Events**

- Change in pattern suggestive of new myocardial infarction.
- Sustained ventricular tachyarrhythmias (>30 seconds' duration).
- Second- or third-degree AV block requiring pacemaker placement.
- Asystolic pauses requiring pacemaker placement.
- Atrial flutter or fibrillation with rapid ventricular response requiring cardioversion.
- Ventricular fibrillation/flutter.
- At the discretion of the investigator, any arrhythmia classified as an adverse experience.

The enumerated list of major events of potential clinical concern are recommended as "alerts" or notifications to the investigator and Pfizer study team, and not to be considered as all inclusive of what to be reported as AEs/SAEs.

## **10.8. Appendix 8: Medical Device Adverse Events, Adverse Device Effects, Serious Adverse Events, and Device Deficiencies: Definition and Procedures for Recording, Evaluating, Follow-up, and Reporting**

### **Definitions of a Medical Device Incident**

The definitions and procedures detailed in this appendix are in accordance with ISO 14155.

Both the investigator and the sponsor will comply with all local medical device reporting requirements.

The detection and documentation procedures described in this protocol apply to all sponsor medical devices provided for use in the study (see [Section 6.1.2](#) for the list of sponsor medical devices).

#### **10.8.1. Definition of AE and ADE**

AE and ADE Definition

• An AE is defined as any untoward medical occurrence, unintended disease or injury, or untoward clinical signs (including abnormal laboratory finding) in study participants, users, or other persons, whether or not related to the investigational medical device. This definition includes events related to the investigational medical device or comparator for study participants, users, and other persons. This definition also includes events considered related to procedures for study participants only.

• An ADE is defined as an adverse event related to the use of an investigational medical device. This definition includes any adverse events resulting from insufficient or inadequate instructions for use, deployment, implantation, installation, or operation, or any malfunction of the investigational medical device as well as any event resulting from use error or from intentional misuse of the investigational medical device.

#### **10.8.2. Definition of SAE, SADE, and Unanticipated Serious Adverse Device Effect**

If an event is not an AE per definition above, then it cannot be an SAE even if serious conditions are met (eg, hospitalization for signs/symptoms of the disease under study, death due to progression of disease).

An SAE is an AE that:
a. Led to death
b. Led to serious deterioration in the health of the participant, that either resulted in: 

• A life-threatening illness or injury. The term “life-threatening” in the definition of “serious” refers to an event in which the participant was at risk of death at the time

of the event. It does not refer to an event, that hypothetically might have caused death, if it were more severe.
 

• A permanent impairment of a body structure or a body function.

• Inpatient or prolonged hospitalization, planned hospitalization for a preexisting condition, or a procedure required by the protocol, without serious deterioration in health, is not considered an SAE.

• Medical or surgical intervention to prevent life-threatening illness or injury or permanent impairment to a body structure or a body function.

c. Led to fetal distress, fetal death, or a congenital abnormality or birth defect.
SADE Definition

• A SADE is defined as an adverse device effect that has resulted in any of the consequences characteristic of a serious adverse event.

USADE Definition

• A USADE is a serious adverse device effect which by its nature, incidence, severity or outcome has not been identified in the current version of the risk analysis management file.

### 10.8.3. Definition of Device Deficiency

Device Deficiency Definition

• A device deficiency is an inadequacy of a medical device with respect to its identity, quality, durability, reliability, safety, or performance. Device deficiencies include malfunctions, use errors, and inadequate labeling.

### 10.8.4. Recording/Reporting and Follow-up of AEs and/or SAEs and Device Deficiencies

AE, SAE and Device Deficiency Recording

• When an AE/SAE/device deficiency occurs, it is the responsibility of the investigator to review all documentation (eg, hospital progress notes, laboratory reports, and diagnostic reports) related to the event.

• The investigator will then record all relevant AE/SAE/device deficiency information in the participant's medical records, in accordance with the investigator's normal clinical practice and on the appropriate form of the CRF.

• It is not acceptable for the investigator to send photocopies of the participant's medical records to Pfizer Safety in lieu of following the reporting process described in the IP manual and completing the Medical Device Complaint CRF.

- There may be instances when copies of medical records for certain cases are requested by Pfizer Safety. In this case, all participant identifiers, with the exception of the participant number, will be redacted on the copies of the medical records before submission to Pfizer Safety.
- The investigator will attempt to establish a diagnosis of the event based on signs, symptoms, and/or other clinical information. Whenever possible, the diagnosis (not the individual signs/symptoms) will be documented as the AE/SAE.
- For device deficiencies, it is very important that the investigator describes any corrective or remedial actions taken to prevent recurrence of the incident.
  - A remedial action is any action other than routine maintenance or servicing of a medical device where such action is necessary to prevent recurrence of a device deficiency. This includes any amendment to the device design to prevent recurrence.

#### **Assessment of Intensity**

The investigator will make an assessment of intensity for each AE/SAE/device deficiency reported during the study and assign it to 1 of the following categories:

- Mild: An event that is easily tolerated by the participant, causing minimal discomfort and not interfering with everyday activities.
- Moderate: An event that causes sufficient discomfort and interferes with normal everyday activities.
- Severe: An event that prevents normal everyday activities. An AE that is assessed as severe should not be confused with an SAE. Severe is a category utilized for rating the intensity of an event; and both AEs and SAEs can be assessed as severe.
- An event is defined as “serious” when it meets at least 1 of the predefined outcomes as described in the definition of an SAE, NOT when it is rated as severe.

#### **Assessment of Causality**

- The investigator is obligated to assess the relationship between study intervention and each occurrence of each AE/SAE/device deficiency.
- A “reasonable possibility” of a relationship conveys that there are facts, evidence, and/or arguments to suggest a causal relationship, rather than a relationship cannot be ruled out.
- The investigator will use clinical judgment to determine the relationship.
- Alternative causes, such as underlying disease(s), concomitant therapy, and other risk factors, as well as the temporal relationship of the event to study intervention administration will be considered and investigated.
- The investigator will also consult the IB in his/her assessment.

- For each AE/SAE/device deficiency, the investigator **must** document in the medical notes that he/she has reviewed the AE/SAE/device deficiency and has provided an assessment of causality.
- There may be situations in which an SAE has occurred and the investigator has minimal information to include in the initial report to the sponsor. However, it is very important that the investigator always make an assessment of causality for every event before the initial transmission of the SAE data to the sponsor.
- The investigator may change his/her opinion of causality in light of follow-up information and send an SAE follow-up report with the updated causality assessment.
- The causality assessment is one of the criteria used when determining regulatory reporting requirements

#### **Follow-up of AE/SAE/Device Deficiency**

- The investigator is obligated to perform or arrange for the conduct of supplemental measurements and/or evaluations as medically indicated or as requested by the sponsor to elucidate the nature and/or causality of the AE/SAE/device deficiency as fully as possible. This may include additional laboratory tests or investigations, histopathological examinations, or consultation with other healthcare providers.
- If a participant dies during participation in the study or during a recognized follow-up period, the investigator will provide Pfizer Safety with a copy of any postmortem findings including histopathology.
- New or updated information will be recorded in the originally completed CRF.
- The investigator will submit any updated SAE data to the sponsor within 24 hours of receipt of the information.

#### **10.8.5. Reporting of SAEs**

##### **SAE Reporting to Pfizer Safety via an Electronic Data Collection Tool**

- The primary mechanism for reporting an SAE to Pfizer Safety will be the electronic data collection tool.
- If the electronic system is unavailable, then the site will use the paper SAE data collection tool (see next section) in order to report the event within 24 hours.
- The site will enter the SAE data into the electronic system as soon as the data become available.
- After the study is completed at a given site, the electronic data collection tool will be taken off-line to prevent the entry of new data or changes to existing data.

- If a site receives a report of a new SAE from a study participant or receives updated data on a previously reported SAE after the electronic data collection tool has been taken off-line, then the site can report this information on a paper SAE form (see next section) or to Pfizer Safety by telephone.

#### **SAE Reporting to Pfizer Safety via CT SAE Report Form**

- Facsimile transmission of the CT SAE Report Form is the preferred method to transmit this information to Pfizer Safety.
- In circumstances when the facsimile is not working, notification by telephone is acceptable with a copy of the CT SAE Report Form sent by overnight mail or courier service.
- Initial notification via telephone does not replace the need for the investigator to complete and sign the CT SAE Report Form pages within the designated reporting time frames.

#### **10.8.6. Reporting of SADEs**

##### **SADE Reporting to Pfizer Safety**

[figure not shown]
NOTE: There are additional reporting obligations for medical device incidents that are potentially related to SAEs that must fulfill the legal responsibility to notify appropriate regulatory authorities and other entities about certain safety information relating to medical devices being used in clinical studies.

- Any device deficiency that is associated with an SAE must be reported to the sponsor within 24 hours after the investigator determines that the event meets the definition of a device deficiency.
- The sponsor shall review all device deficiencies and determine and document in writing whether they could have led to an SAE. These shall be reported to the regulatory authorities and IRBs/ECs as required by national regulations.

## **10.9. Appendix 9: Country-specific Requirements**

Not applicable.

[figure not shown]
## 10.10. Appendix 10: Evaluation of Participants with Decreased Platelet Count

**Management of Participants who D/C Dosing Due to Decreased Platelets:** The PI should obtain a history and physical to evaluate for potential causes of thrombocytopenia such as concomitant medications (eg heparin), intercurrent illnesses, and evidence of bleeding.

[figure not shown]
The PI should obtain CBC with platelets, blood smear, electrolytes, renal and liver function, fibrinogen degradation products, PT, aPTT. Consider obtaining viral serologies for EBV, HIV, hepatitis A, B, C, CMV, mumps, varicella, or rubella in susceptible or symptomatic individuals. Other evaluations may be obtained as indicated. Samples for PK and ADA should be obtained. Platelet counts should be monitored according to the judgment of the Investigator and in consultation of the Medical Monitor until platelet counts stabilize.

### 10.11. Appendix 11: Evaluation of Participants with Worsening Renal Function

\*Potential causes to consider (not inclusive): concurrent use of NSAIDs, antibiotics, or other medications known to effect eGFR; volume depletion; urinary tract infection or obstructive uropathy.

## 10.12. Appendix 12: Management of Elevated AST or ALT

### 10.13. Appendix 13: Alternative Measures During Public Emergencies

The alternative study measures described in this section may be followed during public emergencies, including the COVID-19 pandemic. This appendix applies for the duration of the COVID-19 pandemic globally and will become effective for other public emergencies only upon written notification from Pfizer. This appendix is not intended for use during screening.

Consult with the site monitor prior to utilizing this appendix.

Use of these alternative study measures are expected to cease upon the return of business as usual circumstances (including the lifting of any quarantines and travel bans/advisories).

#### 10.13.1. Eligibility

While SARS-CoV2 testing is not mandated for this study, local clinical practice standards for testing should be followed. Participants with active infections are excluded from study participation as per [Exclusion Criterion 9](#) (other medical condition or laboratory abnormality that may increase the risk of study participation or, in the investigator's judgment, make the participant inappropriate for the study). When the infection resolves, the participant may be considered for re-screening if the participant has not been randomized.

#### 10.13.2. Home Health Visits

A home health care service may be utilized to facilitate scheduled visits per the [Schedule of Activities](#). Home health visits include a healthcare provider conducting an in-person study visit at the participant's location, rather than an in-person study visit at the site. **If the participant does not allow blood draws for laboratory assessments, the participant will be discontinued from study intervention.** The following may be performed during a home health visit:

- Obtain vital signs (seated blood pressure and pulse rate).
- Obtain weight.
- Draw blood for laboratory assessments. (See [Section 10.13.4.1](#) and [Section 10.13.7](#)).
- Collect urine specimen for laboratory assessments. (See [Section 10.13.4.1](#)).
- Perform 12-lead ECG.
- Review and record study intervention, including compliance (review dosing diary, if available) and missed doses.
- Review and record any AEs and SAEs since the last contact. Refer to [Section 8.3](#).
- Review and record any new concomitant medications or changes in concomitant medications since the last contact.

- Review and record contraceptive method and results of pregnancy testing, if applicable. Confirm that the participant is adhering to the contraception method(s) required in the protocol. Refer to [Appendix 4](#) regarding pregnancy tests.

Study participants must be reminded to promptly notify site staff about any change in their health status.

### 10.13.3. Telehealth Visits

In the event that in-clinic study visits or home health visits cannot be conducted, every effort should be made to follow up on the safety of study participants at scheduled visits per the [Schedule of Activities](#) or unscheduled visits. Telehealth visits may be used to continue to assess participant safety and collect data points. **If the participant does not allow blood draws for laboratory assessments, the participant will be discontinued from study intervention.** Telehealth includes the exchange of healthcare information and services via telecommunication technologies (eg, audio, video, video-conferencing software) remotely, allowing the participant and the investigator to communicate on aspects of clinical care, including medical advice, reminders, education, and safety monitoring. The following assessments must be performed during a telehealth visit:

- Review and record study intervention(s), including compliance and missed doses.
- Review and record any AEs and SAEs since the last contact. Refer to [Section 8.3](#).
- Review and record any new concomitant medications or changes in concomitant medications since the last contact.
- Review and record contraceptive method and results of pregnancy testing, if applicable. Confirm that the participant is adhering to the contraception method(s) required in the protocol.

Study participants must be reminded to promptly notify site staff about any change in their health status.

### 10.13.4. Alternative Facilities for Safety Assessments

#### 10.13.4.1. Laboratory Testing

All specimen collections under this appendix will be performed by home health care and will be processed in the central laboratory. It is preferred that participants utilize home health care for safety and efficacy laboratory evaluations. Use of local laboratories will be allowed only if on site or home health care measures cannot be used. If a study participant is unable to visit the site or have home health utilized for protocol-specified laboratory evaluations, testing may be conducted at a local laboratory if permitted by local regulations. The local laboratory may be a standalone institution or within a hospital.

If a local laboratory is used, qualified study site personnel must order, receive, and review results. Site staff must collect the local laboratory reference ranges and

certifications/accreditations for filing at the site. Laboratory test results are to be provided to the site staff as soon as possible. The local laboratory reports should be filed in the participant's source documents/medical records. Relevant data from the local laboratory report should be recorded on the CRF.

If a participant requiring pregnancy testing cannot visit a local laboratory for pregnancy testing or engage in home health care, a home urine pregnancy testing kit with a sensitivity of at least 25 mIU/mL may be used by the participant to perform the test at home, if compliant with local regulatory requirements. The pregnancy test outcome should be documented in the participant's source documents/medical records and relevant data recorded on the CRF. Confirm that the participant is adhering to the contraception method(s) required in the protocol.

#### **10.13.4.2. Imaging**

If the participant is unable to visit the study site for MRI-PDF assessment, the participant may visit an alternative facility to have the MRI-PDF assessment performed. Qualified study site personnel must order, receive, and review results.

#### **10.13.4.3. Electrocardiograms**

All 12-lead ECG assessments under this appendix will be performed by home health care. Qualified study site personnel must order, receive, and review results.

#### **10.13.5. Study Intervention**

If the safety of a trial participant is at risk because they cannot complete required evaluations or adhere to critical mitigation steps, then discontinuing that participant from study intervention must be considered.

Study intervention may be shipped by courier to study participants if permitted by local regulations and in accordance with storage and transportation requirements for the study intervention. Pfizer does not permit the shipment of study intervention by mail. The tracking record of shipments and the chain of custody of study intervention must be kept in the participant's source documents/medical records.

If in-home dosing is instituted, a dosing diary will be provided to the participant for documenting compliance. The dosing diary should be returned to the site for review as soon as possible.

The following is recommended for the administration of study intervention for participants who have active confirmed (positive by regulatory authority-approved test) or presumed (test pending/clinical suspicion) SARS-CoV2 infection:

- For symptomatic participants with active SARS-CoV2 infection, study intervention should be delayed for at least 14 days from the start of symptoms. This delay is intended to allow the resolution of symptoms of SARS-CoV2 infection.

- Prior to restarting treatment, the participant should be afebrile for 72 hours, and SARS-CoV2-related symptoms should have recovered for a minimum of 72 hours. Notify the study team when treatment is restarted.
- Continue to record any concomitant medication administered for treatment of SARS-CoV2 infection.

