Month	-1						1		2	3	4	5	6	8	
Visit Window (Days)					±1	±1	±2	±2	±2	±3	±3	±3	±3	±7	

- a. Day relative to start of study intervention (Day 1).
- b. Screening Period is a maximum of 28 days. Complete all inclusion/exclusion procedures and assessments denoted at Screening Visit 1; placebo injection training may be performed at Screening Visit 1 or Screening Visit 2. After participant has otherwise qualified for the study, including review of lipid and clinical laboratory results and completion of successful placebo training injections, perform MRI-PDFF at Screening Visit 3 or any time prior to randomization.
- c. If participants are not fasted for lipid panel and ApoB collection, perform other Screening activities and have participants return fasted for these tests.
- d. Screening Visit 1 activities should be completed within 7 days.
- e. Occurs 12 weeks after last dose: Week 32 for participants assigned to Q4W regimen or Week 34 for participants assigned to Q2W regimen.
- f. For participants who discontinue the study after Week 24, perform Follow-up procedures; do not perform Early Termination/Discontinuation procedures.
- g. For participants who discontinue study intervention or discontinue the study prior to Week 24, the procedures should be performed. Early Termination/Discontinuation procedures to be performed *as soon as practically possible* after decision to stop study intervention but participants should stay in study with continuation of scheduled visits unless participant withdraws consent from further study participation.
- h. Diary to be dispensed only to participants assigned to Q2W regimen.
- i. Laboratory results from Week 1 visit should be reviewed by the investigator prior to Week 2 dosing for participants dosing Q2W and prior to Week 4 dosing for participants dosing Q4W.
- j. Lipid panel and ApoB should be obtained with participants in a fasted state ([Section 5.3.2](#)). Lipid panel includes non-HDL-C, TG, direct LDL-C, total cholesterol, HDL-C, direct VLDL-C.
- k. Extended lipoprotein panel and FFA should be obtained with participants in a fasted state ([Section 5.3.2](#)). Extended lipoprotein panel includes Lp(a), ApoB-48, ApoB-100, ApoC-III, ApoA-I.
- l. ANGPTL3 should be obtained with participants in a fasted state ([Section 5.3.2](#) and [Section 8.6](#)).

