## **8. STUDY ASSESSMENTS AND PROCEDURES**

The investigator (or an appropriate delegate at the investigator site) must obtain a signed and dated ICD before performing any study-specific procedures.

Study procedures and their timing are summarized in the [SoA](#). Protocol waivers or exemptions are not allowed.

Safety issues should be discussed with the sponsor immediately upon occurrence or awareness to determine whether the participant should continue or discontinue study intervention.

Adherence to the study design requirements, including those specified in the [SoA](#), is essential and required for study conduct.

All screening evaluations must be completed and reviewed to confirm that potential participants meet all eligibility criteria. The investigator will maintain a screening log to record details of all participants screened and to confirm eligibility or record reasons for screening failure, as applicable.

Every effort should be made to ensure that protocol-required tests and procedures are completed as described. However, it is anticipated that from time to time there may be circumstances outside the control of the investigator that may make it unfeasible to perform the test. In these cases, the investigator must take all steps necessary to ensure the safety and well-being of the participant. When a protocol-required test cannot be performed, the investigator will document the reason for the missed test and any corrective and preventive actions that he or she has taken to ensure that required processes are adhered to as soon as possible. The study team must be informed of these incidents in a timely manner.

For samples being collected and shipped, detailed collection, processing, storage, and shipment instructions and contact information will be provided to the investigator site prior to initiation of the study.

The total blood sampling volume for individual participants in this study is approximately 250 mL. The actual collection times of blood sampling may change. Additional blood samples may be taken for safety assessments at times specified by Pfizer, provided the total volume taken during the study does not exceed 550 mL during any period of 60 consecutive days.

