#### **10.13.6. Adverse Events and Serious Adverse Events**

If a participant has COVID-19 during the study, this should be reported as an AE or SAE and appropriate medical intervention provided per standard process. If a participant has positive COVID-19 (SARS-CoV2) test, even if asymptomatic, this should be recorded as an AE (see [Section 8.3](#)).

Study treatment should continue unless the investigator/treating physician is concerned about the safety of the participant, in which case temporary or permanent discontinuation may be required.

It is recommended that the investigator discuss temporary or permanent discontinuation of study intervention with the study medical monitor.

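### Appendix 13 gives two different dosing defaults for a participant with symptomatic, confirmed SARS-CoV2 infection about whom no physician has a safety concern (minor)

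*Protocol*

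**What the plan says.** Both sections sit in Appendix 13, which Amendment 1 added and which applies for the duration of the COVID-19 pandemic, so both are current text.

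- **Protocol 10.13.5 (Study Intervention).** The guidance is introduced as a recommendation: "The following is recommended for the administration of study intervention for participants who have active confirmed" or presumed infection. Its first rule is that, for participants with symptomatic active infection, "study intervention should be delayed for at least 14 days from the start of symptoms". The stated purpose is to let symptoms resolve. Before restart, the participant should have been afebrile for 72 hours and symptoms should have recovered for at least 72 hours. The delay does not depend on a physician's safety concern.
- **Protocol 10.13.6 (Adverse Events and Serious Adverse Events).** This section opens with a participant who has COVID-19 during the study, then adds a positive test even without symptoms. Its dosing rule is: "Study treatment should continue unless the investigator/treating physician is concerned about the safety of the participant". If there is such a concern, temporary or permanent discontinuation may follow. Discussing discontinuation with the medical monitor is recommended.

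Section 10.13.5 contains no cross-reference. Section 10.13.6 refers only to Section 8.3.

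**The concern.** Two adjacent sections of one appendix set a default for the same participant, and the defaults differ. Under 10.13.5 symptoms alone are enough to hold the dose. Under 10.13.6 symptoms are not enough, because a physician must also have a safety concern. A site that opens the protocol at the adverse event section and follows it literally would give an investigational drug during an acute illness in which the preceding section recommends withholding it. What is at stake is uniform handling of acutely ill participants across sites.

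**Working it through.** The plan states no figure on this point. The check is a comparison of the two rules by type of participant, followed by a search for text that reconciles them.

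**Step 1: the two rules by case, assuming no physician has a safety concern**

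| Participant | 10.13.5 | 10.13.6 | Conflict? |
|---|---|---|---|
| Confirmed, symptomatic | Delay at least 14 days | Continue | Yes |
| Presumed (test pending or clinical suspicion), symptomatic | Delay at least 14 days | Not clearly covered: the section speaks of COVID-19 or a positive test | Less explicit |
| Positive test, asymptomatic | No delay rule | Continue | No |

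If a physician does have a safety concern, both sections allow interruption and the conflict disappears.

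**Step 2: is there reconciling text?**

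- Protocol Section 8: "Safety issues should be discussed with the sponsor immediately upon occurrence or awareness to determine whether the participant should continue or discontinue study intervention". This is a route for consultation, not a default.
- Protocol 10.13, introduction: "Consult with the site monitor prior to utilizing this appendix". The same applies.
- Protocol 10.13.1: "Participants with active infections are excluded from study participation". This treats active infection as a risk condition, but for eligibility and not for dosing after randomization.
- Protocol 10.13.6, medical monitor: the recommended discussion concerns discontinuation, so a site that simply continues dosing is not prompted by it.
- Protocol 6.1.1: governs what to do with a dose that is missed or late, not whether to hold one.
- Protocol 7 and 7.1.2: do not mention the question.

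None of these says which section prevails.

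**Step 3: when can the rules differ on a due dose?**

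This is schedule arithmetic only. Inputs:

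- Treatment Days 1 to 168.
- Follow-up is 12 weeks after the last dose, at "Week 32 for participants assigned to Q4W regimen or Week 34 for participants assigned to Q2W regimen" (Schedule of Activities). The last dose is therefore at Week 34 − 12 = 22 (Q2W) or Week 32 − 12 = 20 (Q4W).
- Doses due after Day 1: 11 for Q2W (Weeks 2 to 22) and 5 for Q4W (Weeks 4, 8, 12, 16, 20).
- Windows in the Schedule of Activities: ±1 day at Week 2, ±2 at Weeks 4, 6 and 8, ±3 at Weeks 12, 16 and 20, and ±2 for home doses at Weeks 10, 14, 18 and 22.

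With the minimum 14-day delay, a dose due on day D is caught if onset is 0 to 13 days before D, which is 14 onset days per dose. If its window is ±w, onsets 14 − w to 13 days before D still allow dosing within the window. That leaves 14 − w onset days per dose on which the delay pushes the dose out of window.

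- Q2W: 11 × 14 = 154. Sum of w = 1 + (3 × 2) + (3 × 3) + (4 × 2) = 24. 154 − 24 = 130, and 130/168 = 77.4%.
- Q4W: 5 × 14 = 70. Sum of w = (2 × 2) + (3 × 3) = 13. 70 − 13 = 57, and 57/168 = 33.9%.

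These are shares of calendar onset days under the minimum delay. The 72-hour conditions could lengthen the delay. They show that the sections can prescribe different things for a scheduled dose. They do not count participants.

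**The case against.** The strongest reply is that the two sections can be read together. Section 10.13.5 is the dosing section and gives a specific rule for symptomatic infection. Section 10.13.6 is the adverse event section, and its sentence on continuing can be read as saying that recording COVID-19 as an adverse event does not by itself end treatment. The specific rule would then govern. This is a sensible reading and probably the intended one. But 10.13.6 opens with COVID-19 in general, is not limited to asymptomatic cases, and does not point to 10.13.5.

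A second reply is that postponing a dose is compatible with continuing treatment, since 10.13.6 contrasts continuing with discontinuation and Section 6.1.1 handles late doses separately. This softens the conflict. It does not remove it, because 10.13.5 itself speaks of restarting treatment after the delay, and Section 7 recognizes temporary discontinuation.

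A third is that symptomatic infection is itself a safety concern, in line with 10.13.1, so both sections lead to interruption. Many investigators would take that view. Section 10.13.6 nevertheless leaves it to individual judgement, while 10.13.5 does not.

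It is also fair to say that 10.13.5 is only a recommendation, that sites are told to consult, and that the documents identify no specific harm from a dose given during infection. With a mean terminal half-life of 3 to 5 weeks (Protocol 2.2.4.1), a 14-day hold does not remove exposure. These points stand and keep the matter minor. They do not settle which default applies, since both operative sentences use the same word, should.

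**Conclusion.** The conflict is real, narrow and minor. It arises for a symptomatic participant with confirmed infection when neither the investigator nor the treating physician has a safety concern. It rests on the plain wording of two current sections and on the absence of any text that ranks them.

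A reader might infer three stronger things that the documents do not support:

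- **That every infected participant is affected.** Asymptomatic positives are handled consistently, and for presumed cases the conflict is less explicit.
- **That the onset-day shares (77.4% and 33.9%) measure inconsistent handling.** They describe the dosing calendar. The documents give no infection rate, no rate of physician concern and no basis for how often a site would follow 10.13.6 over 10.13.5.
- **That the Week 24 non-HDL-C comparison is compromised.** Nothing in the documents allows such an effect to be sized, and none is claimed. The consultation steps make divergent handling uncommon.

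**What to change.** Replace the sentence on continuing treatment in Protocol 10.13.6 with three short statements:

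1. Participants with symptomatic, confirmed or presumed active infection have study intervention delayed as set out in Section 10.13.5.
2. All other participants continue study treatment.
3. In either case, a safety concern on the part of the investigator or treating physician may require temporary or permanent discontinuation.

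The third statement matters. The existing discontinuation provision should be kept, and it should apply to delayed participants as well. No change to Section 6.1.1 is needed, because it already covers any dose delayed outside its window. The cost is one clause in the protocol and a notice to sites, with no added visits, procedures or data collection.
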